4.3. Selection of Study Population

4.3.1. Description of Study Population

The study population will include approximately 1025 girls (205 per arm) 9-14 years of age. The study will have two sites recruited from one country in Africa (Ghana) and one country in South/Southeast Asia (Bangladesh).

Final eligibility determination will depend on the results of the medical history, clinical examination, fulfillment of all the inclusion and absence of any of the exclusion criteria, and appropriate understanding of the study and completion of the consent process by parents of all participants and assent of adolescent participants.

4.3.2. Inclusion Criteria for Enrollment

Subjects must meet all of the following criteria to be included in the study:

- 1. A healthy (determined by investigator's assessment following medical history and physical examination) female between the ages of 9 14 years (all inclusive) at time of enrollment
- 2. Ability and willingness to provide parental consent and, if applicable based on local in- country regulations, participant assent.
- 3. Parent/LAR provides informed consent
- 4. Anticipated ability and willingness to complete all study visits and evaluations
- 5. Living within the catchment area of the study without plans to move during the conduct of the study

4.3.3. Exclusion Criteria for Enrollment

Subjects meeting any of the following criteria will be excluded from the study.

- 1. Presence of fever or acute disease on the day of vaccination (oral or axillary temperature $\geq 38^{\circ}$ C)
- 2. If participants have childbearing potential, must not be breastfeeding or confirmed pregnant. Women of childbearing potential is defined as any woman or adolescent who has begun menstruation.
- 3. Receipt of an investigational product within 30 days prior to randomization or planning to participate in another research study involving investigational product during the conduct of this study
- 4. Receipt of blood and/or blood products (including immunoglobulin) in 3 months prior to any

dose of vaccination or blood sampling

- 5. Receipt of a live virus vaccine (varicella virus containing vaccine, any measles, mumps, or rubella virus containing vaccine such as MMR, or yellow fever vaccine but not including live attenuated influenza virus vaccine) 4 weeks prior and after each dose of HPV vaccine
- 6. History of any physical, mental, or developmental disorder that may hinder a participant's ability to comply with the study requirements
- 7. Any malignancy or confirmed or suspected immunodeficient condition such as HIV infection, based on medical history and physical examination
- 8. Receipt of or history of receipt of any medications or treatments that affect the immune system, such as immune globulin, interferon, immunomodulators, cytotoxic drugs or other drugs known to be frequently associated with significant major organ toxicity since six months prior to the first HPV vaccine dose. Receipt of long-term (greater than or equal to 2 weeks) potentially immunosuppressive corticosteroid use within six months prior to HPV vaccine dose 1 and enrollment or anticipated receipt during the study period. Specifically, potentially immunosuppressive corticosteroids are any parenteral corticosteroid, high dose (>800 mcg/day) beclomethasone dipropionate or equivalent medication. Nasal and topical steroids are allowed.
- 9. Allergies to any components of the vaccine
- 10. Current or former participation in HPV vaccine related research.
- 11. Prior receipt of an investigational or licensed HPV vaccine
- 12. Any other condition(s) that in the opinion of the investigator would jeopardize the safety or rights of a participant participating in the trial or would render the participant unable to comply with the protocol.

4.3.4. Criteria for Removal of a Subject from Therapy or Study Assessments

Discontinuation from further vaccination may be at the discretion of the Principal Investigator if it is in the interest of the subject or based on the DSMB safety review. In addition, participants will be discontinued from further vaccination for the following reasons:

- Pregnancy
- Ineligibility (either arising during the trial or retrospectively having been overlooked at screening)
- Significant protocol deviation
- Significant non-compliance with treatment regimen or trial requirements
- An adverse event that requires discontinuation of study treatment or results in inability to continue to comply with trial procedures
- Intercurrent illness or disease or medical treatment that occur during the trial and might influence the study results or ability to continue to comply with trial procedures

A participant who cannot be located after 3 contacts and has missed 2 consecutive visits may be considered lost to follow-up. Any participant who fails to attend the final study visit will also be classified as lost to follow-up.

4.4. Treatments

4.4.1. Treatments Administered

Study Vaccine

Cecolin® administered intramuscularly as 0.5 mL suspension in a single-dose vial.

Comparator/Control Vaccine

Gardasil® administered intramuscularly as 0.5 mL suspension in a single-dose vial.

4.4.2. Method of Assigning Subjects to Treatment Groups (Randomization)

Randomization is defined as the process of assigning a subject to a study arm. Recruited and enrolled subjects will be block randomized in a 1:1:1:1:1 ratio into their assigned treatment group. Randomization will be stratified by site to balance the total subjects in each group from each site. Furthermore, since neutralization assays are labor intensive, technically more complex than Enzyme-Linked Immunosorbent Assay (ELISA) and not currently amenable to high throughput, approximately 20% of subjects from each group will be randomly selected to also participate in the Pseudovirion-based neutralization assay (PBNA) analysis.

Any enrolled subject who is randomized but withdraws for any reason prior to vaccination will be replaced. Subjects who are withdrawn for any reason after vaccination will not be replaced.

4.4.3. Blinding

This is an open-label study.

4.4.4. **Prior and Concomitant Therapy**

Routine vaccinations, which are listed in the exclusion criteria should not be given 4 weeks prior and after each dose of study vaccination. Receipt of an investigational or licensed HPV vaccine is also an exclusion criterion. However, administration of rabies, tetanus, COVID-19 or other types of vaccine for prevention or post-exposure indications will take priority over the study considerations. Such vaccines used during the study will be reported in the Concomitant Medication CRF.

4.4.5. Treatment Compliance

All subjects should receive two vaccinations according to the schedule of the group they are randomized to and the second vaccination should be administered within ± 28 days of the scheduled visit time. Dose preparation and administration for each vaccine will be completed according to manufacturer recommendations and carried out by qualified study staff members with preparation witnessed by another study staff member. At each vaccination visit, the date and time of administration will be recorded on a CRF as well as whether the vaccination was administered fully and per protocol.

4.4.6. **Protocol Deviations**

A protocol deviation is defined as an isolated occurrence involving a procedure that did not follow the study protocol, or study specific procedures. All deviations from the protocol will be recorded on the Protocol Deviation eCRF. There are two types of protocol deviations in this study:

1. A protocol deviation is subject-specific.

2. A Non-Subject Specific protocol deviation is any deviation that is not related to one specific study subject but rather to an incorrect process, procedure, or an issue at the clinic/facility level (e.g., a deviation that applies to a regulatory issue, temperature excursion or an incorrect process affecting multiple subjects at one time).

4.5. Immunogenicity and Safety Variables

The following section describes the collection of immunogenicity and safety variables. For a detailed schedule of activities, refer to Table 1. For a list of the primary and secondary immunogenicity and safety variables, refer to Section 3.2 and Section 9.

4.5.1. Immunogenicity Variables

To evaluate immunogenicity of Cecolin® and Gardasil®, anti-HPV 16 and 18 IgG antibody measured by enzyme-linked immunosorbent assay (ELISA) and anti-HPV 16 and 18 serum neutralizing antibodies measured by pseudovirion-based neutralization assay (PBNA) will be used. For each treatment group, blood will be collected for immunologic testing for the primary endpoint at one month following second dose. Additional blood collections will occur at baseline, immediately prior to the administration of the 6-month, 12-month or 24-month dose, and 24 months after the first dose in Groups 1 and 4 for noninferiority comparison.

4.5.2. Adverse Events

An adverse event (AE) is any untoward medical occurrence in a participant after administration of the investigational vaccine and that does not necessarily have a causal relationship with the investigational vaccine.

4.5.2.1. Solicited Adverse Events

Solicited AEs are pre-specific local and systemic adverse events that are common or known to be associated with vaccination that are actively monitored as indicators of vaccine reactogenicity. For this trial, solicited AEs will be assessed by study staff 30 minutes after each vaccination and then daily for 7 days by the participants (data to be collected for Days 1 through 7). Participants will be provided a memory aid to record the presence or absence of solicited AEs, severity of the solicited AEs and use of concomitant medication.

The following specific solicited adverse events will be monitored for this trial:

Local Reactions:

• Pain, erythema/redness, swelling, induration, pruritus, abscess.

General/Systemic Reactions:

• Fever, headache, vomiting, nausea, fatigue, chills, muscle pain, cough, diarrhea, dizziness, allergic dermatitis, rash, syncope and anorexia.

Unexpected suspected adverse reaction is considered "unexpected" if it is not listed in the investigator brochure or is not listed at the specificity or severity that has been observed (FDA).

4.5.2.4. Serious Adverse Event (SAE) or Suspected Unexpected Serious Adverse Reaction (SUSAR)

Serious adverse event is any adverse event that results in any of the following outcomes:

- 1. Death
- 2. Is life-threatening (life-threatening means that the study participant was, in the opinion of the site PI or Sponsor, at risk of death at the time of the event; it does not refer to an event which hypothetically might have caused death if it were more severe).
- 3. Requires inpatient hospitalization or prolongation of existing hospitalization
- 4. Results in persistent or significant incapacity or substantial disruption of the ability to conduct normal life functions
- 5. Congenital abnormality or birth defect
- 6. Important medical event that may not result in one of the above outcomes but may jeopardize the health of the study participant or (and) require medical or surgical intervention to prevent one of the outcomes listed in the above definition of serious adverse event

SAEs are collected from the time of first vaccination through the end of the study for each.

Suspected unexpected serious adverse reaction (SUSAR) is any suspected adverse reaction that is both unexpected and serious.

4.5.3. Severity of Adverse Events

The severity of all AEs will be assessed by the investigator and participant (as applicable) based on the Division of AIDS (DAIDS) Table for Grading the Severity of Adult and Pediatric Adverse Events, the July National corrected version 2.1. 2017, of US Institute of Health (https://rsc.niaid.nih.gov/sites/default/files/daidsgradingcorrectedv21.pdf). This severity grading criteria provided in Appendix II grade AEs from Mild (Grade 1) to Life Threatening (Grade 4). All AEs leading to death are Grade 5 events. AEs are graded with the worst severity grade during the illness/symptoms.

4.5.3.1. Causality of Adverse Event

The study investigator/s will determine the causal relationship between the study vaccine and the AE. The causality assessment will be made on the basis of the available information at the time of reporting and may be subsequently changed according to follow-up information. Determining of causality will be based on clinical judgment and should take into consideration the following factors:

- Is there a temporal (time-based) relationship between the event and administration of the investigational product?
- Is there a plausible biological mechanism for the investigational product to cause the AE?
- Is there a possible alternative etiology for the AE such as concurrent illness, concomitant medications?
- Are there previous reports of similar AEs associated with the investigational product or other vaccines in the same class?

For this study, the investigator/s will classify the causality of the AE according to the categories defined below:

Related: There is a reasonable possibility that the product caused the event. "Reasonable possibility" means that there is evidence to suggest a causal relationship between the study product and the AE.

Not Related: There is not a reasonable possibility that the administration of the study product caused the event.

5. SAMPLE SIZE CONSIDERATIONS

Immunogenicity:

It is anticipated that no more than 10% of subjects will be seropositive at baseline and that no less than 85% of subjects will be evaluable for the immunogenicity assessments; see Section 6.3 for definitions of the immunogenicity analysis populations.

The primary objective includes three non-inferiority comparisons of Cecolin® at 0 and 6 months, 0 and 12 months, or 0 and 24 months compared to Gardasil® at 0 and 6 months. To control the type I error for the three co-primary non-inferiority hypotheses a Bonferroni correction resulting in a one-sided alpha of 0.0083 and corresponding to 98.3% confidence intervals (CI) will be used. To account for the simultaneous assessment of serotypes 16 and 18, 95% power is required for each comparison to achieve 90% power overall for the primary objective (0.952 \approx 0.90).

Non-inferiority will be demonstrated if the lower bound of the 98.3% CI of the geometric mean concentration (GMC) ratio is greater than 0.5 for both HPV 16 and HPV 18. Assuming an IgG standard deviation of 0.65 of the log10 scale, adjustment for center, 10% baseline seropositive (see Section 3.3), and 15% dropout 205 subjects per arm will result in 90% power overall for the primary non-inferiority comparisons. The non-inferiority margin of 0.5 was selected in accordance with the WHO Technical Report Series #962.

A sample size of 205 in the mixed schedule Gardasil® at 0 months and Cecolin® at 24 months provides 96% power for similar non-inferiority comparisons to Gardasil® at 0 and 6 months for both serotypes at the one-sided alpha 0.025 level. Similarly, the 24-month comparison of the 0,6 Gardasil® and 0,6 Cecolin® groups has greater than 90% power for non-inferiority comparisons for both serotypes at the one-sided alpha 0.025 level.

Analyses of the PBNA data will be descriptive in nature. However, the 20% sub-sample of subjects, resulting in approximately 200 overall for relevant timepoints, will provide a lower bound above 0.6 for the 95% CI for a Spearman's rank correlation of 0.7 or higher.

Safety:

There is greater than 90% power to observe a severe or serious AE at a rate of $\geq 0.4\%$ among the 615 subjects that will receive Cecolin[®] in month 0 and a rate of $\geq 0.6\%$ among the 410 receiving at least one dose of Gardasil[®]. Within any arm there is a greater than 90% probability of observing at least one severe or serious AE with a $\geq 1.2\%$. The upper bounds of the 95% CIs implied if no AEs are observed are shown in Table 2.

6. GENERAL STATISTICAL CONSIDERATIONS

6.1. General Principles

All analyses will be grouped by vaccination arm. In general, all data will be listed, sorted by treatment group, site and subject, and when appropriate by visit number within subject. All summary tables will be structured with a column for each treatment group (including a column for all participants) and will be annotated with the total population size relevant to that table, including any missing observations.

Except where otherwise indicated, summary statistics will be composed of the mean, standard deviation, 1st, 2nd, and 3rd quartile, and the minimum and maximum for continuous variables. For categorical variables, the count and proportion will be presented.

6.2. Timing of Analyses

Safety data of each study arm will be prepared and reviewed by the Protocol Safety Review Team (PSRT) and the Data and Safety Monitoring Board (DSMB). For details, refer to Section 6.6.2 and Section 6.6.3.

Upon collection, shipment, and laboratory analysis of the Month 7 serology sample from the subjects in the 0,6 Cecolin and Gardasil arms, an interim analysis will be initiated. The interim analysis will include, for groups 1 and 4, the analysis of the primary and secondary immunogenicity endpoints and the analysis of the secondary safety endpoints for these two groups. Only the sponsor will receive the report generated by Emmes, and will receive a selection of tables and listings (See section 6.6.1).

A final analysis of all data collected will be performed after all data queries have been resolved and the data base locked.

6.3. Analysis Populations

6.3.1. Enrolled Population

All screened participants who provide informed consent and are randomized regardless of the participant's treatment status in the trial will be included in the enrolled population.

6.3.2. Total Vaccinated Population

All participants in the enrolled population who were randomized and received at least one dose of study vaccination. All safety analyses will be performed using this population. Treatment groups for safety analysis will be assigned according to the actual treatment received at Day 1.

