# 3 STUDY DESIGN

This randomized, active-comparator controlled, open-label Phase 3 study will enroll approximately 1025 girls aged 9 to 14 years in one country in Africa (Ghana) and one country in South/Southeast Asia (Bangladesh).

Subjects will be randomized 1:1:1:1:1 to receive Cecolin® at 0 and 6 months, 0 and 12 months, or 0 and 24 months, Gardasil® at 0 and 6 months, or Gardasil® at 0 months and Cecolin® at 24 months (see Figure 1). For each arm, blood will be collected for immunologic testing at baseline and one month following second dose. Additional blood collections will occur immediately prior to the administration of the 6-month, 12-month or 24-month dose for immunobridging to other published and ongoing trials and 24 months after the first dose in groups 1 and 4 for noninferiority comparison.

Girls of target age will be identified, and their parents contacted to attend an informational session for individual discussion, informed consent, and randomization.

The study will be conducted by two research groups in two selected countries Bangladesh and Ghana.

The vaccination arms will be divided into 5 groups as below:

Group 1: Cecolin® 0 and 6 months

Group 2: Cecolin® 0 and 12 months

Group 3: Cecolin® 0 and 24 months

Group 4: Gardasil® 0 and 6 months (control)

Group 5: Gardasil® 0 months and Cecolin® 24 months

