4. INVESTIGATIONAL PLAN

4.1. Overall Study Design and Plan

This randomized, active-comparator controlled, open-label Phase 3 study will enroll approximately 1025 girls aged 9 to 14 years in one country in Africa (Ghana) and one country in South/Southeast Asia (Bangladesh).

Subjects will be randomized 1:1:1:1:1 to one of the following groups to receive Cecolin[®] and/or Gardasil[®]. Each group will consist of 205 subjects.

- Group 1: Cecolin[®] at 0 and 6 months,
- Group 2: Cecolin[®] at 0 and 12 months,
- Group 3: Cecolin[®] at 0 and 24 months,
- Group 4: Gardasil[®] at 0 and 6 months (control), or
- Group 5: Gardasil[®] at 0 months and Cecolin[®] at 24 months.

For each arm, blood will be collected for immunologic testing at baseline and one month following second dose. Additional blood collections will occur immediately prior to the administration of the 6-month, 12-month or 24-month dose for immunobridging to other published and ongoing trials and 24 months after the first dose in groups 1 and 4 for noninferiority comparison.

The clinical protocol time and events schedule is shown in Table 1, Appendix A and a copy of the study schematic is shown below.

Figure A.1 Study Schematic

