9. SAFETY EVALUATION

All safety assessments will take place in the total vaccinated population, according to the treatment received and will be summarized overall and by study site. All subject-level percentages (solicited/unsolicited AEs etc.) will be supplemented with two-sided 95% CIs computed via the Clopper-Pearson method. Summaries will include all events occurring on or after the date of each vaccination. Individual summaries (denominators for percentages) will be limited to the number of subjects within the appropriate analysis population with data available for analysis for the given endpoint.

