9.1.1. Reactogenicity

- Reactogenicity will be assessed according to immediate (at least 30 minutes post-vaccination) and • delayed reactogenicity (through Day 7), after any and each vaccination. Delayed and immediate solicited AEs will be summarized by category (local/systemic), by reaction and by postvaccination time point, overall and by site (Table 48 through Table 59). Solicited AEs will also be summarized by severity within reaction and within category by post-vaccination time point and by site and by vaccine type (Table 60 through Table 69), and by severity and reaction according to post-vaccination day by post-vaccination time point and by site. The summaries will present each severity up to the maximum severity reported for each reaction/day combination (Table 70 through Table 75). Each subject will be counted only once under the maximum severity of each reaction and/or category, where relevant, in these summaries. Analyses involving severity will include those graded ≥ 2 . Summaries of solicited AEs observed across the solicitation period will be accompanied by a two-sided Fisher exact test p-value for a difference among groups, for both local and systemic events (overall and by reaction), as well as across these events (overall). Reactogenicity events ongoing at 7 days post-vaccination will be listed (Listing 12). Duration of reactogenicity events will be summarized by reaction and time period and by site (after any dose, after first dose and after second dose) (Table 76 through Table 81).
- Measured injection site features will be summarized by group and post-vaccination time point, including but not limited to erythema/redness, swelling, and induration (Table 82 through Table 85).

Individual listings of solicited AEs ongoing at 7 days after any dose will be generated (Listing 12).

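### Assigning safety groups by the Day 1 treatment cannot define the five arms or place a girl given the wrong product, and the after-dose-2 denominators for unsolicited events conflict

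*SAP*

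**What the plan says.** The rule for safety groups is one sentence, identical in SAP 6.3.2 and protocol 11.4.2: "Treatment groups for safety analysis will be assigned according to the actual treatment received at Day 1".

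SAP 9, repeated in 9.1, gives a broader basis with no limit to Day 1: "All safety assessments will take place in the total vaccinated population, according to the treatment received and will be summarized overall and by study site". Protocol 11.5.2.2 carries the same broader wording.

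The design has five arms (SAP 4.1): "Subjects will be randomized 1:1:1:1:1 to one of the following groups to receive Cecolin[®] and/or Gardasil[®]. Each group will consist of 205 subjects". Groups 1, 2 and 3 start with Cecolin; Groups 4 and 5 start with Gardasil. One arm changes product by design (protocol section 3): "Group 5: Gardasil® 0 months and Cecolin® 24 months".

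The safety endpoints in SAP 3.2.2.2 are counted per study arm, with solicited and unsolicited events counted after each dose. SAP 6.1 gives every summary table one column per treatment group. SAP 9.1.1 reports reactogenicity after each vaccination as well as after any, and tabulates solicited events by severity "by site and by vaccine type (Table 60 through Table 69".

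On denominators, SAP 9 restricts percentages to girls with data for the endpoint concerned. SAP 9.1.2 instead divides unsolicited-event counts by the group's total vaccinated population, and applies this to tables that include summaries by post-vaccination time point.

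**The concern.** The arms differ in when dose 2 is given and, between Groups 4 and 5, in which product it is. The product given on Day 1 shows none of this. Read literally, the rule produces two groups where the tables need five.

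For a girl dosed as planned this does no harm, because her arm is known from randomisation. The rule matters only when treatment received differs from treatment assigned, and that is where it gives no answer (wrong product on Day 1) or keeps the Day 1 label (wrong product at dose 2). In an open-label trial the choice would then be made by someone who can see the events.

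The denominator question is separate and does not depend on errors. A girl who never received dose 2 cannot have an event after it. Counting her in the denominator lowers the reported rate, and lowers it more in arms that lose more girls before dose 2.

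**Working it through.** **1. The plan's own safety figures.** Inputs are the group sizes and rates in protocol 11.3 (including Table 2) and SAP 5. The chance of at least one event is 1 − (1 − p)^n. The two-sided 95% upper bound with no events is 1 − 0.025^(1/n).

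| n | rate p | chance of at least one event | upper bound, no events |
|---|---|---|---|
| 615 | 0.4% | 91.5% | 0.60% |
| 410 | 0.6% | 91.5% | 0.90% |
| 205 | 1.2% | 91.6% | 1.78% |

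All agree with the stated figures (above 90%; bounds 0.6%, 0.9%, 1.8%). Nothing in this point disturbs them.

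**2. What the Day 1 rule can separate.** With 205 per arm, Cecolin on Day 1 is 3 × 205 = 615 girls and Gardasil is 2 × 205 = 410. That is two groups.

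**3. Product errors under each wording.**

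| Case | SAP 6.3.2 | SAP 9 and 9.1 |
|---|---|---|
| Group 1, 2 or 3 girl given Gardasil on Day 1 | Group 4 or 5, undetermined | not specified |
| Group 4 or 5 girl given Cecolin on Day 1 | Group 1, 2 or 3, undetermined | not specified |
| Group 4 girl given Cecolin at month 6 | stays under Gardasil | may be read as Cecolin after dose 2 |

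The documents give no expected number of such errors, so their numerical effect cannot be calculated.

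**4. By-product tables, under a condition.** At full dosing, girls who start with Gardasil receive 410 × 2 = 820 doses. Of these, the 205 second doses in Group 5 are Cecolin. If the by-vaccine-type tables used the Day 1 product, the share of doses labelled Gardasil that are really Cecolin would be:
- all doses: 205 / 820 = 25%;
- second doses: 205 / 410 = 50%.

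The supplied SAP text does not define vaccine type, and the shells for Tables 60-69 are not in it, so the condition cannot be checked.

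**5. Denominator.** If a share m of an arm misses dose 2 and the true rate among recipients is r, dividing by the whole arm reports r × (1 − m). The value of r is illustrative. For m, 15% borrows the planned dropout in SAP 5; it is not a stated figure for missed second doses. With r = 20%:
- m = 5%: 20% × 0.95 = 19%;
- m = 10%: 20% × 0.90 = 18%;
- m = 15%: 20% × 0.85 = 17%.

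If a month-6 arm lost 5% and a month-24 arm 15%, equal true rates of 20% would show as 19% and 17%, a difference made only by the denominator.

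**The case against.** The strongest reply is that the plan as a whole handles the planned switch. Group 5 is a defined treatment group with its own column, reactogenicity is shown after each vaccination, and the serious-event listing in SAP 9.2 gives the prior dose received. This stands. A reader might infer from the Day 1 sentence that the plan ignores the Group 5 switch or credits that arm's Cecolin reactions to Gardasil throughout. The documents do not support that: the Group 5 after-dose-2 column is the safety record of Cecolin after Gardasil.

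A reader might also take 25% or 50% as the size of the problem. That requires the by-vaccine-type tables to use the Day 1 product. The Day 1 sentence speaks of treatment groups, and vaccine type is a different term.

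Product errors are also guarded against. Vials carry the participant's number and preparation is witnessed (protocol 5.3). A second staff member checks the assignment and vaccine on Day 1 (6.2.2), and assignment is verified at dose 2 (6.2.5, 6.2.9, 6.2.12). Deviations and vaccine administration are listed (SAP 7.2 and 7.4). Some errors are remote: no arm is due Gardasil at month 24. So errors should be few, but a rule for errors must still say what to do with one.

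Finally, SAP 9 can be read as the general statement and 6.3.2 as its detail. That is a fair reading and makes the mismatch imprecision rather than open contradiction. It does not help a girl given the wrong product on Day 1, and it settles dose-2 errors in favour of the earlier product.

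**Conclusion.** The rule is wrong as written for this design and should be corrected, but its reach is limited. In the five-arm tables it affects only girls given a wrong product. Their number is unknown and probably small, and girls dosed as planned are reported correctly. The 25% and 50% shares remain conditional on a table definition that cannot be seen, and should not be quoted as the effect.

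The denominator in SAP 9.1.2 conflicts with SAP 9 and needs no error to matter. It understates after-dose-2 unsolicited-event rates by the share of girls who miss dose 2: 20% becomes 17% if that share is 15%, which is an assumption. Arms with a month-24 second dose would be affected more only if they lose more girls before it.

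No figure for the primary immunogenicity objective changes: sample size, alpha and power are untouched.

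**What to change.** Use the same wording in SAP 6.3.2, SAP 9 and 9.1, and protocol 11.4.2:

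- **Safety group.** The randomised arm, unless the full product sequence and schedule actually received match another arm. A Group 5 girl given Cecolin at months 0 and 24 would then count in Group 3. A Group 1 girl given Gardasil and then Cecolin at month 6 matches no arm and stays in Group 1.
- **After-dose-1 and after-dose-2 tables.** Keep all five arm columns. Attributing these tables to product alone would collapse the arms and pool Group 5's second dose with those of Groups 1-3.
- **Tables by vaccine type.** Attribute each event to the product last received before onset.
- **Denominators.** In after-dose-2 tables, including unsolicited events in SAP 9.1.2, count only girls who received dose 2.
- **Listing.** Show every girl whose received sequence differs from her assignment.

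The cost is one derived variable and slightly more programming. Vaccination dates are already recorded (SAP 4.4.5) and the product administered is in the accountability records (protocol 5.4). The protocol sentence needs ethics approval as an amendment (protocol 13.1). The remaining compromise is that a girl whose sequence matches no arm stays in a column that does not fully describe what she received; the listing makes that visible.
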